#### 2.2.5 Worst-case

[figure not shown]
A worst-case analysis visit will be created for the combined treatment and follow-up phase for parameters for which abnormalities and/or toxicity grades are defined to summarize values considered as the worst-case over time. For abnormalities, this visit is derived per parameter and in case both the lowest and the highest values are considered abnormal, a participant can have two worst-case analysis visits for a same parameter. For toxicity grades, the worst-case is the value associated to the highest toxicity grade and is derived per parameter and toxicity direction (hypo/hyper).

All non-missing post-baseline values in the treatment and follow-up phase, including unscheduled assessments, will be considered when deriving the worst-case analysis visit.

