3. OBJECTIVES AND ENDPOINTS

Objectives	Endpoints				
Primary					
• To assess the safety of treatment, extended treatment, and retreatment with efgartigimod PH20 SC in participants with PV or PF	• Incidence and severity of treatment-emergent adverse events (TEAEs), adverse events of special interest (AESIs), and serious adverse events (SAEs) by system organ class (SOC) and preferred term (PT)				
	• Vital sign measurements, physical examinations, electrocardiograms (ECGs), and clinical laboratory safety evaluations				
Secondary					
• To evaluate the efficacy of efgartigimod PH20 SC treatment in PV and PF	Proportion of PV participants who achieve CRmin				
	• Proportion of PV and PF participants who achieve CRmin				
	• Time to DC				
	• Time to CR				
	• Time to CRmin				
	• Time to CRoff				
	• Time to flare				
	• Rate of treatment failure				
	• Rate of flare				
	• Cumulative prednisone dose over the trial				
	• Pemphigus Disease Area Index (PDAI) at each visit				
• To assess the health impact of glucocorticoid (GC) use in participants with PV or PF	• Composite Glucocorticoid Toxicity Index (C-GTI) comprising the Aggregate Improvement Score (AIS) and the Cumulative Worsening Score (CWS)				
• To evaluate the effects of efgartigimod PH20 SC on quality of life (QoL) in participants	• EuroQol 5-Dimension 5-Level (EQ-5D-5L) score				
with PV or PF	• Autoimmune Bullous Disease Quality of Life (ABQOL) score				
• To evaluate the pharmacokinetics (PK) of efgartigimod PH20 SC in participants with PV or PF	• Efgartigimod serum concentrations				
• To evaluate the PD of efgartigimod PH20 SC in participants with PV or PF	• Total IgG and subtype (IgG1, IgG2, IgG3, IgG4) serum levels				
	• Anti-Dsg-1 and -3 autoantibodies serum levels				

Objectives	Endpoints			
• To evaluate the immunogenicity of efgartigimod in participants with PV or PF	• Incidence and prevalence of antidrug antibodies (ADA) against efgartigimod (serum levels)			
• To explore feasibility of self-administration of efgartigimod PH20 SC	• Percentage of participants who performed self-administration			
	• Percentage of caregivers who administered the injection to the participant			
	• Number of visits needed for the participant or caregiver to be competent to start administering efgartigimod PH20 SC			
	• Frequency of self- or caregiver-supported administration at home			
Exploratory				

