9.3. Sample Size Determination

Not applicable for this OLE trial.

9.4. **Populations for Analysis**

The following populations are defined:

Population	Description
Safety set	All participants who received at least 1 dose, or part of a dose, of IMP
Rollover set	All participants who rolled over from the ARGX-113-1904 study

The safety set is used for safety analysis (except for the analysis of C-GTI and GTI-SL). In general, the rollover set is used for efficacy evaluation (according to the treatment the participant was randomized to in the ARGX-113-1904 study). All details on the specific analysis of an endpoint in a specific population will be provided in the SAP.

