# **DEFINITION OF TERMS**

Case report form (CRF)	A printed, optical, or electronic document designed to record protocol required information to be reported to the sponsor for each study participant.
Complete clinical remission (CR)	The absence of new lesions and complete healing of established lesions (except for post-inflammatory hyperpigmentation or erythema from resolving lesions).
Complete remission on minimal therapy (CRmin)	The absence of new and established lesions completely healed while the participant is receiving prednisone therapy at $\leq 10$ mg/day for at least 2 months (8 weeks).
Complete remission off therapy (CRoff)	The absence of new and established lesions completely healed while the participant is receiving no prednisone therapy for at least 2 months (8 weeks).
Disease control (DC)	The absence of new lesions and the start of healing of established lesions.
Disease progression	Increase of $\geq$ 5 points in the PDAI activity score, observed at any post-baseline visit before DC.
Display	Analysis table, listing or figure
End of consolidation (EoC)	The time at which no new lesions have developed for a minimum of 2 weeks and approximately 80% of lesions have healed.
Flare	The appearance of 3 or more new lesions in a 4-week period that do not heal spontaneously within 1 week or the extension of established lesions, in a participant who had achieved DC.
Phase	Interval of time in the planned conduct of a study that is associated with a specific purpose: for example, screening, treatment, follow-up.

SGS	Statistical Analysis Plan		
ARGX-113-1905	Final analysis	Final 1.0 of 26APR2024	
Significant digit	All digits of a number used to express it to the required degree of accuracy, starting from the first non-zero digit.		
Standardized unit	unit populating –STRESU in the clinical database		
Study drug or investigational medicinal product (IMP)	Pharmaceutical form of an active ingredient or placebo, being tested or used as a reference in a clinical study.		
Treatment-emergent abnormality / toxicity	Any post-baseline abnormality/toxicity that was not present at baseline (e.g. hemoglobin normal or missing at baseline and grade 1 post-baseline; glucose low at baseline and high post-baseline; QTcF ]450; 480] ms at baseline and >500 ms post-baseline)		

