#### Table 1: Phase, period and subperiod definition

Document template OTH.STAT.010 v3

CONFIDENTIAL AND PROPRIETARY

System Version: 1.0, Status: Approved, Document ID: VV-TMF-172580

SGS	Statistical Analysis Plan	
ARGX-113-1905	Final analysis	Final 1.0 of 26APR2024

Treatment period 1 is only applicable for participants who did not achieve CRmin or CRoff in 1904

Treatment	Treatment period 1 b,c	On-treatment 1	Earliest of (date of signing the informed consent form (ICF) of study 1905 and date of roll-over), with 00:00 added as time part a .	For the participants with off- treatment 1 subperiod : last IMP administration date/time in treatment period 1. For other participants: Date of week 52/EoT/ET visit, with 23:59 added as time part.
			1	For participants who don't have a week 52/EoT/ET visit: date of last contact, with 23:59 added as time part.
		Off-treatment 1	administration date/time in treatment period 1	For the participants with a next treatment period: first IMP administration date/time in next treatment period – 1 minute.
			+ 1 minute	For other participants:
			Date of week 52/EoT/ET visit, with 23:59 added as time part.	
			For participants who don't have a week 52/EoT/ET visit: date of last contact, with 23:59 added as time part.	
	Treatment n	eriod 2 is applicab	le for participants with	flare after CRmin in the roll-over

Treatment period 2 is applicable for participants with flare after CRmin in the roll-over phase or in treatment period 1 and who re-initiate IMP administration

Treatment period 2 °	On-treatment 2	First IMP administration date/time in treatment period 2	For the participants with off- treatment 2 subperiod : last IMP administration date/time in treatment period 2.
			For other participants:
			Date of week 52/EoT/ET visit, with 23:59 added as time part.
			For participants who don't have a week 52/EoT/ET visit: date of last contact, with 23:59 added as time part.

Page 18 of 84

SGS	Statistica	al Analysis Plan		
ARGX-113-1905	F	inal analysis		Final 1.0 of 26APR2024
	Off-treatment 2	Last IMP administration date/time in treatment period 2	trea adm	the participants with a next tment period: first IMP ninistration date/time in next tment period – 1 minute.
		+ 1 minute For	For	other participants:
				e of week 52/EoT/ET visit, h 23:59 added as time part.
			wee last	participants who don't have a ek 52/EoT/ET visit: date of contact, with 23:59 added as e part.
Etc c				

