Follow-up		End of treatment phase + 1 minute		e of last contact, with 23:59 ed as time part.

a In case no 1905 ICF date is available, participant data will not be considered in the analysis

b Not applicable for participants who enter 1905 on CRmin. They will start immediately in Treatment period 2 of the Treatment phase in case of flare

A new treatment period is considered for participants with a flare after achieving CRmin (ie, while being off IMP treatment). A new treatment period is not considered after temporary IMP discontinuation for an adverse event. Repeat until the last on-treatment or off-treatment subperiod.

Participants who enter 1905 on CRmin, will not have a treatment period 1 in the treatment phase, but will start immediately with treatment period 2 at first IMP intake in 1905 (ie, after the first flare in 1905). Note: treatment period 2 is defined in 1905 as the treatment period starting after the first flare within 1905. Treatment given before a first flare in 1905 is considered belonging to treatment period 1.

Adverse events (AEs) and concomitant therapies will be allocated to phases and periods as described in sections 5.1.2 and 3.3.2 respectively. All other assessments will be allocated to phases (PDAI, PD, PK, albumin and LDL-C also to periods and subperiods) based on the assessment date(time).

In case of (partially) missing date(time) fields disabling allocation, information from the visit/timepoint label and protocol schedule of activities will be used to allocate to the correct phase, period and subperiod. If this is not possible (unscheduled visits or visits on a turning point between phases, periods or subperiods), assessments will be handled as follows:

- Treatment phase vs. roll-over phase: assessments will be allocated to the treatment phase unless the available parts of the assessments start or stop date/time provide evidence for allocating to the roll-over phase.
- Treatment phase vs. follow-up phase: assessments will be allocated to the treatment phase unless the available parts of the assessments start or stop date/time provide evidence for allocating to the follow-up phase.
- On-treatment vs. off-treatment subperiod within a treatment period: assessments will be allocated to the on-treatment subperiod unless the available parts of the assessments start or stop date/time provide evidence for allocating to the off-treatment subperiod.

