#### 5.1.2 Derivation rules

Treatment-emergent adverse events (TEAE) are defined as AEs starting on or after any administration of IMP in 1905 up through 60 days after the last administration of IMP prior to the AE.

Post-treatment AEs are defined as AEs that start after the 60 days after the last IMP administration prior to the AE. AEs that start during the roll-over phase are also considered as post-treatment AEs

Based on their start date/time, AEs will be allocated to the phase in which they started. Each AE will therefore be reported in only one phase. Phases are defined in section 2.2.1. In case the AE start date/time is incomplete or missing, and the AE could consequently be allocated to more than one phase, a worst-case allocation will be done in following order:

- Treatment phase vs. roll-over phase: the AE will be allocated to the treatment phase unless the available parts of the AE start and stop date/time provide evidence for allocating to the roll-over phase.
- Treatment phase vs. follow-up phase: the AE will be allocated to the treatment phase unless the available parts of the AE start and stop date/time provide evidence for allocating to the follow-up phase.

A death case is defined as an AE with outcome 'fatal'.

An AE for which the IMP was discontinued is defined as an AE with action taken 'drug withdrawn'.

Treatment relatedness will be dichotomized as follows in tables:

- Treatment related: related, probably related, possibly related or missing
- Not treatment related: not related, unlikely related

Page 49 of 84

SGS	Statistical Analysis Plan	
ARGX-113-1905	Final analysis	Final 1.0 of 26APR2024

Adverse events of special interest will be defined using MedDRA system organ class 'Infections and infestations'.

Injection-related reactions (IRRs) will be defined as all AEs with MedDRA preferred terms that are listed in either:

- Hypersensitivity standardized MedDRA query (SMQ) (broad selection)
- Anaphylactic reaction (SMQ) (broad selection)
- Extravasation events (injections, infusions and implants) (SMQ) (broad selection), excluding implants

AND occurring within 48 hours of an administration, or within 2 days in case no AE start time is available. In case of partially missing AE start date, the AE will be considered as an IRR, unless the available parts of the AE start date provide evidence it did not occur within 48 hours of an injection.

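### New lab and vital-sign abnormalities (and worst-case, Week 52 and follow-up ECG) stay treatment-emergent with no limit after the last dose, while AEs become post-treatment after 60 days

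*SAP*

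**What the plan says.** Protocol Section 3 puts these measures in the primary endpoint, next to adverse events: "Vital sign measurements, physical examinations, electrocardiograms (ECGs), and clinical laboratory safety evaluations".

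**Abnormalities.** The SAP's Definition of terms describes a treatment-emergent abnormality or toxicity as "Any post-baseline abnormality/toxicity that was not present at baseline", without reference to time since dosing. SAP 2.2.5 builds the worst case over the treatment and follow-up phases together: "All non-missing post-baseline values in the treatment and follow-up phase, including unscheduled assessments, will be considered when deriving the worst-case analysis visit". The resulting counts go into the lab, vital-sign and ECG tables (SAP 5.2.3, 5.3.3, 5.4.3).

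**Adverse events.** SAP 5.1.2 counts an AE as treatment-emergent only "up through 60 days after the last administration of IMP prior to the AE". After that: "Post-treatment AEs are defined as AEs that start after the 60 days after the last IMP administration prior to the AE". SAP 5.1.3 then gives treatment-emergent, post-treatment and overall displays.

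**Phases.** IMP stops at CRmin (Protocol 4.1), but the treatment phase does not. For participants with no further treatment period, SAP Table 1 ends it at the "Date of week 52/EoT/ET visit, with 23:59 added as time part". The off-treatment subperiods therefore lie inside the treatment phase. The text after Table 1 uses those subperiods for a few parameters only: "All other assessments will be allocated to phases (PDAI, PD, PK, albumin and LDL-C also to periods and subperiods) based on the assessment date(time". For the rest, SAP 2.2.4 assigns visit windows by day in phase, whether or not dosing continues.

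**The concern.** Two rules for the same word operate within the primary safety analysis, and nothing in the SAP reconciles them. Three consequences follow from the rules.

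- A new lab or vital-sign abnormality seen long after the last dose is counted as treatment-emergent.
- The same event can carry two labels. Protocol 8.3.6 requires clinically significant lab abnormalities to be recorded as AEs, with an exception when they fit a current diagnosis. Beyond 60 days the AE is post-treatment, while the lab value behind it is treatment-emergent.
- By-visit rows for vital signs, and for labs other than albumin and LDL-C, combine participants on weekly efgartigimod with participants who stopped at CRmin. The first follow-up row likewise combines people dosed up to week 52 with people off drug since CRmin. An on-drug effect that reverses would look smaller in these rows.

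The SAP already treats off-drug data as different elsewhere. It removes off-treatment PK after CRmin from the descriptive statistics (4.2.1), and it splits PDAI, PD, albumin and LDL-C by subperiod (2.2.4, Table 5). It gives no reason for leaving the other labs and vital signs pooled.

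**Working it through.** The plan states no figure on this point. Sample size is "Not applicable for this OLE trial" (Protocol 9.3) and no hypothesis is tested (Protocol 9.2). The check therefore compares the rules and counts calendar time.

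**1. Rules side by side**

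| | AEs | Labs, vital signs, ECG |
|---|---|---|
| Treatment-emergent until | 60 days after last preceding dose (SAP Table 2, 5.1.2) | end of follow-up (Definition of terms, 2.2.5) |
| Later findings | post-treatment | no separate category |
| Displays | treatment-emergent, post-treatment, overall | one |
| On-/off-treatment split by visit | not applicable | albumin and LDL-C descriptives only |

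**2. Time beyond the 60-day window**

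Inputs: CRmin at week c; last dose taken as week c−1; no retreatment; end of study at week 56 for participants whose treatment ended before week 49 (Protocol Section 8); 60 days = 60/7 = 8.57 weeks. The values of c are illustrative.

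Weeks off drug = 56 − (c−1). Weeks beyond the window = that − 8.57. Share = weeks beyond / 56.

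| c | Weeks off drug | Weeks beyond window | Share of 56 weeks |
|---|---|---|---|
| 20 | 37 | 28.4 | 51% |
| 26 | 31 | 22.4 | 40% |
| 40 | 17 | 8.4 | 15% |

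**3. Effect on a worst-case count when the drug does nothing**

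Assumptions: a constant, independent chance p of a new abnormality per visit; visits every 4 weeks, plus weeks 52 and 56; last dose at week 12, 20 or 30; no retreatment. In each case there are 14 post-baseline visits, of which 5, 7 or 9 fall within the 60-day rule and 9, 7 or 5 fall after it.

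Proportion with at least one abnormality = 1 − (1−p)^k, where k is the number of visits counted. With p = 1%:

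- current rule, k = 14: 13.1%
- 60-day rule, k = 5, 7, 9: 4.9%, 6.8%, 8.6%
- ratio: 2.7, 1.9, 1.5

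For p from 0.5% to 5% the ratio runs from 2.7 to 2.3 (week 12), 2.0 to 1.7 (week 20) and 1.5 to 1.4 (week 30). Participants on the Protocol Table 2 schedule have weekly labs at first, so more on-drug values; for labs their ratio would be smaller.

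**4. Effect on a by-visit mean**

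If a share f of a row is off drug and the effect has fully reversed (assumption), an on-drug mean change D appears as (1−f)·D: 0.8·D at f = 0.2, 0.6·D at f = 0.4, 0.4·D at f = 0.6.

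**5. ECG**

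Under Protocol Table 1 (footnote g), participants not receiving efgartigimod have ECGs only at baseline and end of study. Under Table 2 (footnote h), ECGs are three-monthly while on drug, plus start of retreatment, CRmin and end of study. Off-drug ECGs therefore enter mainly through the Week 52 and follow-up windows and the worst case.

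**The case against.** The strongest reply has five parts.

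- **No effect to dilute is documented.** Protocol 2.3.1 reports no clinically significant vital-sign or ECG changes to date, and none in liver enzymes, lipids or electrolytes in healthy, MG or ITP participants. This stands. Dilution is a possibility that the rules create, and the documents do not show that it happens.
- **Important abnormalities reach the AE tables anyway**, where the 60-day split applies. This is largely true, but it is also how the conflicting labels arise, and it does not correct the lab and vital-sign counts.
- **Taking every value is conservative, and timing can be traced in the listings.** That defends an overall count. It does not defend calling the count treatment-emergent, and it does not help the by-visit means, which can move the other way. It is a good reason not to discard the late values.
- **Retreatment after a flare reopens the window**, so the shares in step 2 apply only to participants who are not retreated. This stands.
- **Part is already handled.** Roll-over-phase safety data are not tabulated (SAP 2.4.3), and albumin and LDL-C descriptives are split. This stands, although albumin toxicity grades still follow the unlimited rule.

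A reader might go further and infer that ECG rows are mixed throughout. The ECG schedule does not support that. A reader might also express the late weeks as a share of off-drug time only (28.4/37 = 77% for CRmin at week 20). That overstates the matter, because the worst case spans all post-baseline time.

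**Conclusion.** The inconsistency is real for labs and vital signs, and for worst-case, Week 52 and follow-up ECG. Followed as written, the plan can label off-drug abnormalities treatment-emergent on a primary safety measure and can contradict the AE label for the same event. It also pools on- and off-drug participants by visit for vital signs and for labs other than albumin and LDL-C.

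The span concerned is about 28, 22 or 8 weeks (51%, 40% or 15% of 56 weeks) for CRmin at week 20, 26 or 40 without retreatment. The resulting bias cannot be sized from the documents. It depends on when participants reach CRmin, how many are retreated, how fast any effect reverses, and background rates. The ratios in step 3 and the factors in step 4 are illustrations under stated assumptions.

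A reader might infer that drug effects are in fact hidden, or that error rates suffer. The documents support neither: no such effect is reported for the pooled parameters, and all analyses are descriptive. The point should still be corrected, because the labels will be read as attribution to the drug.

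**What to change.** 1. Apply the existing SAP Table 2 subperiods to labs, vital signs and ECG. Base the treatment-emergent flag, and a treatment-emergent worst case, on post-baseline values from the first 1905 dose to 60 days after the last preceding dose. Amend the Definition of terms and SAP 2.2.5 to say so.
2. Tabulate later new abnormalities as post-treatment.
3. Keep the present all-values worst case, relabelled as overall, so that late values are not lost. The three displays then match those for AEs in SAP 5.1.3.
4. Show by-visit lab and vital-sign descriptives by on- and off-treatment subperiod, as already planned for albumin and LDL-C.

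The cost is SAP wording, reuse of subperiod definitions that already exist, and more table pages. The pages multiply through the Japanese, Mainland Chinese and East Asian repeats (SAP 2.4), where some cells will be small. No new data collection is needed.

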#### 2.3 IMPUTATION AND ROUNDING RULES

#### 2.3.1 Missing values

For imputation on missing values related to efficacy, see appropriate section of the applicable efficacy endpoint.

# 2.3.2 Handling partially or completely missing dates in calculations

Prednisone administration start dates with partially missing data will be imputed as follows:

- Missing day will be imputed with first day of the month or start date of the first phase, whichever comes latest.
- Missing day and month will be imputed with 1JAN or start date of the first phase, whichever comes latest.
- Completely missing date will be imputed with start date of the first phase.

Prednisone administration end dates with partially missing data will be imputed as follows:

- Missing day will be imputed with last day of the month or the date of last contact, whichever comes first.
- Missing day and month will be imputed with 31DEC or the date of last contact, whichever comes first.
- Completely missing end date will be considered as still ongoing at the end of the study.

[figure not shown]

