# 3.4.2 Derivation rules

The following parameters will be derived for EFG PH20 SC treatment periods and administrations:

- Number of re-treatment periods: number of treatment periods excluding treatment period 1, i.e.:
  - 0: for participants without any treatment period or only treatment period 1
  - 1: for participants with treatment period 2
  - 2: for participants with treatment period 2 and 3
  - o Etc.
- Number of administrations: sum of all administrations of study drug.
- Number of loading doses: i.e. daily doses of of 1000 mg).

The following parameters will be derived for prednisone administration:

- NCPD (in mg/kg/day)
- Cumulative prednisone dose (in mg)

Result will be rounded as detailed in section 2.3.4

SGS	Statistical Analysis Plan	
ARGX-113-1905	Final analysis	Final 1.0 of 26APR2024

The NCPD will be calculated based on prednisone equivalent doses. The prednisoneequivalent dose is calculated as [dose of ATC]\*[equivalence factor prednisone]/[equivalence factor ATC]. Following [equivalence factors] are used:

- Betamethasone [1.5]
- Cortisone [37.5]
- Deflazacort [15]
- Dexamethasone [1.5]
- Fluocortolone [10]
- Hydrocortisone [30]
- Methylprednisolone [8]
- Methylprednisolone acetate [8]
- Methylprednisolone sodium succinate [8]
- Paramethasone [4]
- Prednisolone [10]
- Prednisolone acetate [10]
- Prednisolone sodium succinate [10]
- Prednisone [10]
- Prednisone acetate [10]
- Prednylidene [12]
- Rimexolone [20]
- Triamcinolone [8]

Example: calculation of equivalent dosage of 12 mg methylprednisolone: 12\*10/8=15 mg prednisone.

Only systemic use of oral medication is included.

NCPD (mg/kg/day) is calculated for different periods (see section 3.4.3) as [the sum of (equivalent doses taking into account daily dose frequency)/(body weight in kg)]/(period duration in days) with body weight of visit closest before or at each start of prednisone equivalent medication record. If for a given day, no record exists in the CRF indicating prednisone use on that day, the dose will be assumed to be 0 mg.

Similarly, the cumulative prednisone dose (in mg) over these periods will be calculated based on the prednisone equivalent dose.

SGS	Statistical Analysis Plan	
ARGX-113-1905	Final analysis	Final 1.0 of 26APR2024

The following rules will be applied to allocate prednisone administrations to the correct period:

- Only start and stop dates (not times) will be considered

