- Records with (partially) missing dates will be imputed as detailed in section 2.3.2.
- If administration date records overlap, then the doses reported in all the overlapping records will be combined.
- If an administration is reported as dose per administration with frequency, then the doses should be allocated to the correct dates, taking the start date and the frequency into account. Example:
  - o Dose: 40 mg
  - Frequency: every other day
  - o Start Stop date: 01JAN2022 03JAN2022

This will result in:

- 40 mg be allocated to 01JAN2022
- $\circ$  0 mg allocated to 02JAN2022
- 40 mg allocated to 03JAN2022
- Regardless of the time information, an administration on the day of the start of a new treatment period will only be allocated to that new treatment period, not to the period before.

The following parameters will be derived for IMP (self-)administration by participant and by caregiver:

- Number of participants/caregivers receiving the (self-)administration training.
- Number of training visits received by participant/caregiver.
- Number of participants/caregivers who were adequately trained and capable to (self-)administer EFG PH20 SC.
- Number of training visits before being considered capable to (self-)administer.

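### A non-final prednisone taper step with no end date is run to the end of the study and added to the later steps, which inflates that participant's cumulative dose and NCPD

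*SAP*

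**What the plan says.** SAP 3.4.1 describes each continuous prednisone administration as a record with a start, an end and one dose (a daily total, or a dose per administration with a frequency). A change of dose therefore needs a new record.

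SAP 2.3.2 deals with missing dates. For end dates: "Completely missing end date will be considered as still ongoing at the end of the study". For partial end dates: "Missing day will be imputed with last day of the month or the date of last contact, whichever comes first". A missing day and month goes to 31 December or last contact. Start dates are moved the other way: a missing day to the first of the month, and a wholly missing date to the start of the first phase.

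SAP 3.4.2 then allocates doses to periods: "Records with (partially) missing dates will be imputed as detailed in section 2.3.2"; "Only start and stop dates (not times) will be considered"; and "If administration date records overlap, then the doses reported in all the overlapping records will be combined". NCPD is the sum of weight-adjusted equivalent doses divided by the period length. "Similarly, the cumulative prednisone dose (in mg) over these periods will be calculated based on the prednisone equivalent dose". On a day without any record, "the dose will be assumed to be 0 mg".

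Neither section closes a record when a later one starts, limits the ongoing rule to the last record, or caps the combined daily dose. SAP 2.3.5 rules out outlier detection. Cumulative prednisone dose is a secondary endpoint in Protocol section 3. NCPD is an added endpoint in SAP 6.1. Both are marked for the topline tables in SAP 8.1.

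**The concern.** Protocol 6.5.1 and Table 4 taper prednisone in steps of two weeks down to 20 mg/day and one week below that. A participant will therefore have many short records in sequence. If an early step has no end date, the imputation stretches it across every later step, and the overlap rule adds its dose to each of them. That overlap comes from the imputation and does not reflect tablets taken together.

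These imputation rules can only lengthen a record, so the resulting error is upwards. Prednisone sparing is part of the stated rationale for the treatment, and these two endpoints describe it.

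**Working it through.** The plan gives no figure for the effect of imputation, so there is none to reproduce. The two worked examples in SAP 3.4.2 do reproduce: 12 x 10 / 8 = 15 mg, and 40, 0, 40 mg for alternate-day dosing. The second also shows that the stop date counts as a dosing day.

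**Inputs**
- Doses at 75 kg (Protocol Table 4): 35 mg (0.5 mg/kg), then 20, 17.5, 15, 12.5 and 10 mg.
- Step lengths (Protocol 6.5.1): 14 days at 20 mg, 7 days each at 17.5, 15 and 12.5 mg, and at least 56 days at 10 mg.
- Participation: 60 weeks = 420 days, or 56 weeks = 392 days if treatment ended before week 49 (Protocol section 8).
- Assumption: 8 weeks (56 days) at 35 mg before tapering. The documents do not fix this length.

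**Formulas**
- Excess (mg) = dose of the open record x days from its true end to the end of participation.
- NCPD = total mg / weight / days.

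**True course, 420 days, 10 mg kept to the end**
35 x 56 + 20 x 14 + 17.5 x 7 + 15 x 7 + 12.5 x 7 + 10 x 329 = 5,845 mg. NCPD = 5,845 / 75 / 420 = 0.19 mg/kg/day.

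**One record left open**

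| Open record | True last day | Surplus days | Excess (mg) |
|---|---|---|---|
| 35 mg | 56 | 364 | 12,740 |
| 20 mg | 70 | 350 | 7,000 |
| 17.5 mg | 77 | 343 | 6,002.5 |
| 15 mg | 84 | 336 | 5,040 |
| 12.5 mg | 91 | 329 | 4,112.5 |

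With the 35 mg record open, the total is 5,845 + 12,740 = 18,585 mg (3.2 times the truth). NCPD is 18,585 / 75 / 420 = 0.59. With 330 surplus days instead, the excess is 35 x 330 = 11,550 mg.

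**Range for non-final steps.** This covers 50 to 100 kg, both participation lengths, and starts at 0.5 or 1.5 mg/kg. A 1.5 mg/kg start is assumed to be held for 35 days, with 56 days later at 0.5 mg/kg.
- Smallest: 12.5 x (392 - 182) = 2,625 mg.
- Largest: 150 x (420 - 35) = 57,750 mg.

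**Partial end date.** Month end adds at most 30 days: 35 x 30 = 1,050 mg. Fifteen days at 20 mg adds 300 mg.

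**Missing start date.** A 10 mg step that truly began on day 92 but is moved to day 1 adds 10 x 91 = 910 mg.

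**Changeover days.** If sites enter a stop date equal to the next start date at every step, the excess is 35 + 20 + 17.5 + 15 + 12.5 = 100 mg, or 1.7% of 5,845 mg.

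**Effect on a table.** One excess of 12,740 mg moves a group mean by 12,740 / n:
- 60 mg at n = 213, the maximum in SAP 1.3
- 127 mg at n = 100
- 1,274 mg in a disease-status subgroup of 10 (assumed size)

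The SD is more sensitive. One value d above n - 1 otherwise equal values gives an SD of d / √n, which is 1,274 mg at n = 100. The median barely moves.

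**The case against.** The end-date rule is sound for its obvious use, a last record still running when the participant leaves. Harm needs a non-final step with a blank end date to survive to database lock, and the protocol has controls against that:
- Stop dates are required for concomitant medication (6.5).
- The investigator records the daily prednisone dose since the last visit (8.2).
- Data are checked for completeness and queried, and the investigator approves each eCRF before lock (10.1.10).
- The prednisone listing planned in SAP 3.4.3 would show a 35 mg record running beside a 10 mg one.

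This stands as far as frequency goes: the documents do not say how many records will be affected. It does not remove the point, because the SAP specifies what happens to whatever remains, and that rule gives a wrong value.

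It is also fair that the SAP never says doses are summed. Summing is the natural reading, since it suits genuine concurrent use, but it should be written down.

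A reader might infer that each taper is double-counted on changeover days. The documents do not show how sites enter those dates, so the 100 mg is conditional. A reader might also infer that the reported prednisone results as a whole will be inflated by thousands of mg. That does not follow: the figures are per affected participant, medians and quartiles are reported too (SAP 2.4.1), and the summaries up to CRmin or CRoff stop earlier, which limits the excess there.

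**Conclusion.** The point holds as a fault in a written derivation rule. An undated non-final step overstates that participant's cumulative dose, by 2,625 to 57,750 mg across the cases worked, and overstates NCPD with it (0.59 against 0.19 mg/kg/day in the 75 kg example). This rests on reading the overlap rule as a sum and on the assumed weeks at the starting dose.

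The consequence for the report is limited. Efficacy is descriptive and no hypothesis is tested, so no error rate or decision rule is touched. The exposure is in means, SDs, maxima and small disease-status subgroups, and its likelihood is unknown.

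One wording point belongs with it. Protocol 4.4 defines the end of the study as the last participant's last visit, whereas the partial-date rules use the participant's last contact. The phases in SAP Table 1 end no later than last contact, so this should not change the sums, but the text should agree.

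**What to change.** In SAP 2.3.2:
- Cap an imputed end date at the day before the next later-starting sequential record of the same prednisone-equivalent drug.
- Treat a missing end date as ongoing, to the participant's date of last contact, only if no later record exists or the record is positively identified as ongoing and concurrent. SAP 3.3.1 describes an ongoing flag for therapies in general. SAP 3.4.1 mentions none for prednisone, so its availability must be confirmed.
- Do not let an imputed start date fall on or before the end of the prior sequential record.

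In SAP 3.4.2:
- State that combining means summing, and that it applies to recorded concurrent use and not to overlap created by imputation.
- If a sequential step's recorded stop date equals the next step's start date, count only the new dose that day. This takes precedence over summing.

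With the cap, the 75 kg example returns to 5,845 mg and 0.19 mg/kg/day. Two cases remain for query. The first is an open last record that had really stopped: 10 mg stopped on day 147 but left open adds 10 x 273 = 2,730 mg. The second is a switch between equivalent products, which a same-drug cap would miss.

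The cost is a few sentences and a small programming change, with no new data collection.
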